	
Recheck CPK at least once a week. If CPK remains Grade 3 or decreases, continue cobimetinib at current dose and schedule.

For Grade 4 CPK elevations that are asymptomatic and deemed not clinically significant	
Hold atezolizumab and cobimetinib. Rule out immune-related cardiomyopathy, myocarditis or other cardiac conditions. Workup should generally include ECG, serum cardiac troponin, and CPK-isoforms M and B fraction.
 
Recheck CPK within 3 days. When CPK is Grade ≤ 3 and cardiac immune-related cardiomyopathy has been ruled out, atezolizumab and cobimetinib may be resumed with a dose reduction of cobimetinib by 1 dose level on the same schedule (e.g., 60 to 40 mg).
 
If Grade 4 CPK elevation recurs after 1 dose reduction, cobimetinib may be reduced by another dose level (e.g., 40 to 20 mg).
 
Permanently discontinue cobimetinib if Grade 4 CPK elevation recurs after 2 dose reductions of cobimetinib. Atezolizumab may be continued after consultation with the trial PI.

IM = intramuscular.

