7.3.4 Adverse Events of Special Interest

Adverse events of special interest are required to be reported by the investigator to the Sponsor immediately (i.e., no more than 24 hours after learning of the event). Adverse events of special interest for this study include the following:

- Pneumonitis [atezolizumab]
- Colitis [atezolizumab]
- Endocrinopathies: diabetes mellitus, pancreatitis, adrenal insufficiency, hyperthyroidism or hypophysitis [atezolizumab]
- Systemic lupus erythematosus [atezolizumab]
- Neurologic: Guillain-Barré syndrome, myasthenic syndrome or myasthenia gravis, meningoencephalitis [atezolizumab]
- Nephritis [atezolizumab]
- Events suggestive of hypersensitivity, infusion-related reactions, cytokine release syndrome, influenza-like illness, systemic inflammatory response syndrome, and systemic immune activation [atezolizumab]
- Ocular events
 - Retinal vein occlusion [cobimetinib]
 - Serous retinopathy, including events of retinal detachment, retinal pigment epithelium detachment, neurosensory retinal detachment, and central serous chorioretinopathy [cobimetinib]
 - Ocular inflammatory toxicities (e.g., uveitis, retinitis) [atezolizumab]
- Significant muscular toxicities
 - Rhabdomyolysis or Grade ≥ 3 CPK elevation [cobimetinib]
 - Myopathies including myositis [atezolizumab]
 - Grade ≥ 3 hemorrhage or any grade cerebral hemorrhage [cobimetinib]
 - Grade ≥ 3 rash [cobimetinib and atezolizumab]
- Grade ≥ 2 cardiac events including:
 - Symptomatic heart failure or Grade ≥ 3 left ventricular ejection fraction reduction [cobimetinib]
 - Myocarditis, pericarditis, or atrial fibrillation [atezolizumab]
- Vasculitis [atezolizumab]
- Significant liver toxicity [concern for cobimetinib and atezolizumab]
 - Hepatitis, including AST and/or ALT $> 10 \times \text{ULN}$
 - Cases of potential drug-induced liver injury that include an elevated ALT or AST

in combination with either an elevated bilirubin or clinical jaundice, as defined by Hy's law:

- Treatment emergent ALT or AST $> 3 \times$ ULN in combination with either an elevated total bilirubin ($> 2 \times$ ULN) or clinical jaundice, without initial findings of cholestasis (elevated serum alkaline phosphatase)
- No other reason can be found to explain the combination of increased ALT/AST and total bilirubin, such as: liver metastasis; viral hepatitis A, B, or C; alcoholic and autoimmune hepatitis; other liver diseases; or exposure to other drugs known to cause liver injury

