10. STUDY CALENDAR

Physical examinations and laboratory testing may be completed up to 7 days prior to Day 1 dosing. In the event that the patient's condition is deteriorating, laboratory evaluations should be repeated within 48 hours prior to initiation of the next cycle of therapy.

Patients receiving atezolizumab will be assessed for pulmonary signs and symptoms on physical examination as well as imaging throughout the study.

	Pre-Study	Cycle 1 (28 Days)			Cycle 2 and beyond (28 Days)		Off Study ^N
		Day 1	Day 15	Day 21	Day 1	Day 15	
Visit window ^A	-14 to -1	+/ -2	+/ -2	+/ -5	+/ -2	+/ -2	+/ -7
Informed consent	X						
Demographics	X						
Medical history ^B	X						
Concomitant medications	X	X			X		
Physical exam ^C	X	X	X		X		X
Vital signs ^D	X	X	X		X	X	X
Height	X						
Weight	X	X			X		X
Performance status	X	X			X		X
CBC w/diff ^E	X	X	X		X	X	X
Serum chemistry ^E	X	X	X		X	X	X
Coagulation (INR and aPTT)	X						
Thyroid function test ^F	X				X		
EKG	X						
B-HCG ^G	X						
CPK	X				X ^O		
ECHO or MUGA ^H	X ^H	1 month after first dose, then every 3 months on cobimetinib (see ^H)					
Ophthalmologic exam ^I	X ^I	Every 2 months for 1 year, then every 6 months while on cobimetinib (see ^I)					
Adverse event evaluation		X	X		X		X ^P
Tumor measurements ^J	X	Tumor measurements are repeated every 8 weeks. Documentation (radiologic) must be provided for patients removed from study for progressive disease if possible.					X ^Q
CEA and CA 19-9 ^E	X	X			X		X
Archival tumor sample	X						
Tumor biopsy ^K	X			X			
Peripheral blood for research ^L (up to 50cc)		X ^L	X		X ^L (C2D1 Only)		X
Atezolizumab		X	X		X	X	
Cobimetinib ^M		[---Oral daily in the morning on days 1–21 of a 28-day cycle---]					
Medication Diary		X			X		

A: Longer durations to be approved by the Study Principal Investigator.

B: Includes history of lung disease, HIV, hepatitis B or C infection, and complete cancer history, including primary site of cancer, gross location of primary tumor, secondary sites of cancer, histology, histologic grade, date of initial diagnosis, date of metastatic diagnosis, and prior cancer therapy regimens.

C: Complete physical exam will be completed at baseline; focused physical examinations will be conducted thereafter. Physical examinations should be performed within a window of up to 7 days prior to dosing on days 1 and 15 of cycle 1 and day 1 for all subsequent cycles.

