D: Temperature, respiration rate, blood pressure, pulse, and pulse ox should be taken prior to the administration of atezolizumab.

E: Serum Chemistry should include Glucose, Calcium, Sodium, Potassium, CO₂, Chloride, BUN, Creatinine, Alkaline phosphatase, Alanine amino transferase (ALT), aspartate amino transferase (AST), Bilirubin, Albumin, and Total Protein. Labs may be collected within a window of up to 7 days prior to dosing. Initial screening bloodwork does not need to be repeated if performed within 7 days of C1D1. CEA and/or CA19-9 do not need to be repeated in the event that the screening lab draw show that the patient's tumor does not secrete CEA and/or CA19-9.

F: Free T3/T4 should be checked reflexively if TSH is abnormal.

G: Serum or urine pregnancy (women of childbearing potential only). For women with a mildly elevated B-HCG who in the opinion of the investigator are not pregnant, a vaginal ultrasound must be obtained to confirm that the participant is not pregnant in order to enroll on this study.

H: Baseline evaluation of LV function by either echocardiogram (ECHO) or multiple-gated acquisition (MUGA) will be performed for all participants < 4 weeks prior to randomization (study arms A and B). Repeat ECHO and MUGA 1 month after first dose

(visit window +/- 7 days), then every 3 months (visit window +/- 7 days), while on cobimetinib only (*study arm B only*).

I: Ophthalmologic examination will be performed for all participants < 4 weeks prior to randomization (*study arms A and B*). Repeat ophthalmologic examination will be performed every 2 months for 1 year, then every 6 months while on cobimetinib (visit window +/- 14 days); (*study arm B only*). Eye exam should include retinal exam, slit lamp exam, and visual fields (preferably Humphrey Visual Field or Goldmann Visual Field, if available) for evidence of retinal pathology and other abnormalities. Patients with ocular symptoms occurring during study treatment should be examined by an ophthalmologist

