J: Baseline scans must be done < 4 weeks prior to randomization. Tumor measurement will be performed with contrast CT chest/abdomen/pelvis. Non-contrast CT chest/abdomen/pelvis or CT Chest and MRI Abdomen/pelvis will be performed in subjects with contraindications or intolerance to contrast dye. Imaging will be repeated every 8 weeks (+/- 4 days), irrespective of dosing schedule or treatment delays. For patients continuing treatment past progression, the subsequent scan should be performed 6-8 weeks following the initial scan demonstrating progression (see section 5.3.1.). If this repeat scan does not show further progression, imaging frequency can revert to every 8 weeks (+/- 4 days).

K: Only for subjects with tumor that in the opinion of the study treatment team is safely accessible for biopsy.

L: Baseline research blood collection will be collected prior to dosing of any study therapy (visit window day -7 to 0, prior to dosing). Additional on-treatment research bloods will be collected on cycle 1 day 15 (day -4 to 0), on cycle 2 day 1 (day -4 to 0), and at the time of progression (+/- 7 days). No research blood is needed for day 1 of any cycle beyond cycle 2. Research blood samples should be collected and shipped on Monday-Thursday only to avoid problems with weekend/holiday delivery. For additional details, see section 9.3.1.

M: For patients randomized to cobimetinib plus atezolizumab (*study arm B only*).

N: Off-study evaluations will be completed 4 weeks after meeting at least one of the criteria listed in section 5.3.

O: Patients receiving cobimetinib (*study arm B only*).

P: Adverse events will be assessed at least 90 days after the last dose of either study agent. For patients removed due to unacceptable toxicity, they will be followed until resolution of the adverse event.

Q: Scans do not need to be repeated if a scan has been performed within 8 weeks.

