APPENDIX E PATIENT MEDICATION DIARY - COBIMETINIB

PATIENT ID	
CYCLE NUMBER	

INSTRUCTIONS TO THE PATIENT:

1. Complete one form for each 4 week-period while you take **cobimetinib**. Each cycle of therapy is 4 weeks (28 days).
2. Take your dose of **cobimetinib** at about the same time each morning for the first 21 days. Do not take cobimetinib on days 22 through 28.
3. Record the date, the number of tablets you took, and when you took them. Record doses as soon as you take them; do not batch entries together at a later time.
4. If you miss taking your dose and remember within 1 hour of your scheduled dose, you may take it late. If it has been more than 1 hour, do not make up the dose; resume dosing with the next scheduled dose. If vomiting occurs, do not make up the dose; resume dosing with the next scheduled dose.
5. Take cobimetinib tablets orally in the morning with or without food. The tablets should be swallowed whole and must not be crushed or broken.
6. If you have any comments or notice any side effects, please record them in the Comments column. If you make a mistake while you write, please cross it out with one line, put your initials next to it, and then write the corrected information next to your initials. Example:
~~10:30 am~~ SB *9:30 am*
7. Please return this form to your physician when you go for your next appointment.

Day	Date	Time of Daily Dose	# of Tablets Taken	Comments
1				
2				
3				
4				
5				
6				
7				
8				
9				
10				
11				
12				
13				
14				
Day	Date	Time of Daily Dose	# of Tablets Taken	Comments

15				
16				
17				
18				
19				
20				
21				
22		Do not take cobimetinib on these days.		
23				
24				
25				
26				
27				
28				
Participant's Signature		Date		

Physician's Office will complete this section:

1. Total number of tablets taken this month (each size)

2. Physician/Nurse/Data Manager's Signature/Date

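### No routine CPK is scheduled while cobimetinib is being taken, so transient asymptomatic elevations that Sections 6.3 and 7.3.4 act on may be missed in Arm B

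*Combined protocol and SAP*

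**What the plan says.** **When CPK is measured.** The CPK row of the Section 10 calendar has two marks: pre-study, and Day 1 of Cycle 2 and beyond. Footnote O limits the second to Arm B. The row is blank on Days 1, 15 and 21 of Cycle 1, on Day 15 of later cycles, and at the off-study visit. Serum chemistry is drawn on Day 1 and Day 15 of every cycle, but footnote E itemises that panel and CPK is not in it.

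**When the draw may be taken.** The text above the calendar says "Physical examinations and laboratory testing may be completed up to 7 days prior to Day 1 dosing", and footnote E says "Labs may be collected within a window of up to 7 days prior to dosing". The visit window for Day 1 of Cycle 2 and beyond is ±2 days.

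**When the drug is taken.** The cobimetinib row reads "Oral daily in the morning on days 1–21 of a 28-day cycle", and the patient diary in Appendix E instructs "Do not take cobimetinib on days 22 through 28".

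**What depends on CPK.** The cobimetinib adverse event list in Section 7.1.1.2 puts CPK increase in the Likely (>20%) column. Section 6.3 covers elevations that are asymptomatic and judged clinically unimportant. At Grade 3 both drugs are held for a cardiac work-up, and then: "Recheck CPK at least once a week. If CPK remains Grade 3 or decreases, continue cobimetinib at current dose and schedule". At Grade 4 both drugs are held, CPK is rechecked within 3 days, and cobimetinib resumes one dose level lower. Section 7.3.4 lists "Rhabdomyolysis or Grade ≥ 3 CPK elevation [cobimetinib" among the events to be reported within 24 hours.

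**The concern.** An asymptomatic CPK elevation is found only by testing. The rechecks in Section 6.3 begin once an elevation is already known, so they do not provide first detection. If every routine test falls in the treatment break, a rise that appears and subsides around the dosing days need never be recorded. The Section 6.3 steps and the Section 7.3.4 report would then not be triggered, and the patient would start the next 21 days of drug with the event unseen.

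The reported safety results are also affected. Safety and tolerability is a secondary objective (1.2.3). Section 13.5.1 tabulates events by grade, models their rate by negative binomial regression, and models time to first toxicity by a Cox model. All of these depend on when CPK is looked for. On the nominal schedule, routine testing cannot date a first CPK elevation before study Day 22.

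**Working it through.** The plan gives no figure for CPK detection, so there is none to reproduce. The check is calendar arithmetic followed by an illustration.

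**Step 1: draw days.** Inputs: last cobimetinib dose on Day 21 (calendar, Appendix E); cycle length 28 days, so Cycle 2 Day 1 is nominally study Day 29; draw allowed from 7 days before dosing (calendar text, footnote E); visit window ±2 days.

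Earliest draw = visit day − 7. Days since last dose = draw day − 21.

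| Cycle 2 Day 1 visit | Permitted draw days | Days since last dose | Draw days on drug |
|---|---|---|---|
| Day 27 (−2) | 20–27 | −1 to 6 | 20 and 21 |
| Day 29 (nominal) | 22–29 | 1 to 8 | none |
| Day 31 (+2) | 24–31 | 3 to 10 | none |

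The last row assumes that cobimetinib restarts at that visit. The same arithmetic repeats in each later cycle. On the nominal schedule, the number of routine CPK draws on Days 1–21 of any cycle is 0.

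**Step 2: how much of an on-drug rise would still be visible.** The documents give no rate at which CPK falls after cobimetinib stops. I assume that the excess decays exponentially from Day 21 and vary the half-life h from 1 to 14 days:

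share remaining = 0.5^(days since last dose / h)

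| Assumed h | Day 22 (1 day off) | Day 25 (4 days off) | Day 29 (8 days off) |
|---|---|---|---|
| 1 day | 50% | 6% | 0.4% |
| 2 days | 71% | 25% | 6% |
| 3 days | 79% | 40% | 16% |
| 7 days | 91% | 67% | 45% |
| 14 days | 95% | 82% | 67% |

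For example, h = 1 on Day 29 gives 0.5^8 = 0.004, and h = 14 on Day 29 gives 0.5^(8/14) = 0.67. The loss of signal runs from almost complete to modest, depending on the unknown half-life and on which permitted day is used.

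**Step 3: how many patients could be concerned.** With 82 enrolled (Section 13.2) and equal allocation, Arm B has 82/2 = 41 patients. The 20% bound gives 0.20 × 41 = 8.2, so roughly 8 or more patients with a CPK increase of any grade. This is not a Grade ≥3 count; the documents give no such rate for CPK.

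**The case against.** The strongest reply is that there is no literal contradiction. Sections 6.3 and 7.3.4 say what to do once an elevation is known; neither requires a test during dosing. That is correct. The issue is a gap between the schedule and the rules that depend on it.

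A reader might infer that the trial will under-detect CPK toxicity and that its Arm B rate is biased low. The documents do not support that strength. It needs a decline rate that they do not give, and with a half-life of 7–14 days 45%–67% of the excess is still there on Day 29. A fall off drug is plausible, since the Grade 4 rule holds treatment, rechecks within 3 days and allows resumption at Grade 3 or below. That supports a direction but not a size.

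A reader might also infer that all testing sits at the end of the break. It does not: Day 22 is allowed on the nominal schedule, and an early visit could reach Days 20–21. Those are permitted timings, but nothing in the calendar steers the draw towards them.

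There is partial cover. The Day 15 panel includes creatinine, potassium, calcium and albumin, which Section 6.3 uses in ruling out rhabdomyolysis. Cycle 1 Day 15 has an examination and adverse event review. CPK is part of the work-up for decreased LVEF, and symptoms can prompt an unscheduled test. None of this finds an isolated asymptomatic rise, so the gap is confined to that case.

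The expected number is also uncertain. The single-agent results in Section 2.2.2.2 do not name CPK among events in at least 10% of patients or among the most frequent Grade 3–4 events. Finally, dose steps for asymptomatic CPK apply only at Grade 4, no stopping rule uses CPK, and Arm A has no on-treatment CPK, so neither the primary result nor a between-arm CPK comparison is at stake.

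**Conclusion.** The concern holds in a limited form. If the calendar is followed exactly on the nominal schedule, each on-study CPK is drawn 1–8 days after the last cobimetinib dose. None is planned during dosing, and Cycle 1 has none before its break begins. Transient asymptomatic elevations that Sections 6.3 and 7.3.4 act on may therefore be missed, and the Arm B CPK toxicity rate may be understated.

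The timing result rests on the documents alone. The size of any under-detection is unknown: the range of 0.4%–67% remaining on Day 29 and 50%–95% on Day 22 depends wholly on the assumed half-life of 1–14 days and on the assumption that decay starts at the last dose. The documents do not say that the timing was chosen to fall in the break. This affects patient monitoring and a secondary safety objective; the PFS analysis is untouched.

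**What to change.** Reconcile the CPK row of the calendar with Sections 6.3 and 7.3.4, so that the test those rules depend on is scheduled at a time that can detect on-drug elevations. If sampling in the break is intended, state why it is sufficient. Arm B already has a chemistry draw on Day 15 of every cycle, so the analyte could be added there without a new visit or needle stick; the choice of schedule is for the sponsor.

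Whatever schedule is kept, record and report each CPK result with its draw day relative to the last cobimetinib dose, so that a low observed rate can be read in that light.

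The cost is one extra analyte, some additional asymptomatic elevations to record and work up, and possibly more holds under the existing Section 6.3 rules. This point does not address the management rules themselves.

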11. MEASUREMENT OF EFFECT

11.1 Antitumor Effect – Solid Tumors

For the purposes of this study, patients should be re-evaluated for response every 8 weeks. Response and progression will be evaluated in this study using the new international criteria proposed by the revised Response Evaluation Criteria in Solid Tumors (RECIST) guideline (version 1.1) (Eisenhauer *et al.*, 2009). Changes in the largest diameter (unidimensional measurement) of the tumor lesions and the shortest diameter in the case of malignant lymph nodes are used in the RECIST criteria.

This study will [also] evaluate response and progression using immune-related response criteria (irRC) (Wolchok *et al.*, 2009). See **Appendix D** for a detailed description of the evaluation criteria.

11.1.1 Definitions

Evaluable for toxicity. All patients will be evaluable for toxicity from the time of their first treatment with cobimetinib or atezolizumab.

Evaluable for objective response. Only those patients who have measurable disease present at baseline, have received at least one cycle of therapy, and have had their disease re-evaluated will be considered evaluable for response. These patients will have their response classified according to the definitions stated below. (Note: Patients who exhibit objective disease progression prior to the end of cycle 1 will also be considered evaluable.)

Evaluable Non-Target Disease Response. Patients who have lesions present at baseline that are evaluable but do not meet the definitions of measurable disease, have received at least one cycle of therapy, and have had their disease re-evaluated will be considered evaluable for non-target disease. The response assessment is based on the presence, absence, or unequivocal progression of the lesions.

11.1.2 Disease Parameters

Measurable disease. Measurable lesions are defined as those that can be accurately measured in at least one dimension (longest diameter to be recorded) as ≥ 20 mm (≥ 2 cm) by chest x-ray or as ≥ 10 mm (≥ 1 cm) with CT scan, MRI, or calipers by clinical exam. All tumor measurements must be recorded in millimeters (or decimal fractions of centimeters).

Note: Tumor lesions that are situated in a previously irradiated area may not be considered measurable unless there is evidence of progression in the irradiated site.

Malignant lymph nodes. To be considered pathologically enlarged and measurable, a lymph node must be ≥ 15 mm (≥ 1.5 cm) in short axis when assessed by CT scan (CT scan

slice thickness recommended to be no greater than 5 mm [0.5 cm]). At baseline and in follow-up, only the short axis will be measured and followed.

Non-measurable disease. All other lesions (or sites of disease), including small lesions (longest diameter <10 mm [<1 cm] or pathological lymph nodes with ≥ 10 to <15 mm [≥ 1 to <1.5 cm] short axis), are considered non-measurable disease. Bone lesions, leptomeningeal disease, ascites, pleural/pericardial effusions, lymphangitis cutis/pulmonitis, inflammatory breast disease, and abdominal masses (not followed by CT or MRI), are considered as non-measurable.

Note: Cystic lesions that meet the criteria for radiographically defined simple cysts should not be considered as malignant lesions (neither measurable nor non-measurable) since they are, by definition, simple cysts.

‘Cystic lesions’ thought to represent cystic metastases can be considered as measurable lesions, if they meet the definition of measurability described above. However, if non-cystic lesions are present in the same patient, these are preferred for selection as target lesions.

Target lesions. All measurable lesions up to a maximum of 2 lesions per organ and 5 lesions in total, representative of all involved organs, should be identified as **target lesions** and recorded and measured at baseline. Target lesions should be selected on the basis of their size (lesions with the longest diameter), be representative of all involved organs, but in addition should be those that lend themselves to reproducible repeated measurements. It may be the case that, on occasion, the largest lesion does not lend itself to reproducible measurement in which circumstance the next largest lesion which can be measured reproducibly should be selected. A sum of the diameters (longest for non-nodal lesions, short axis for nodal lesions) for all target lesions will be calculated and reported as the baseline sum diameters. If lymph nodes are to be included in the sum, then only the short axis is added into the sum. The baseline sum diameters will be used as reference to further characterize any objective tumor regression in the measurable dimension of the disease.

Non-target lesions. All other lesions (or sites of disease) including any measurable lesions over and above the 5 target lesions should be identified as **non-target lesions** and should also be recorded at baseline. Measurements of these lesions are not required, but the presence, absence, or in rare cases unequivocal progression of each should be noted throughout follow-up.

